#### **Secondary outcome variable(s)**

SECONDARY OUTCOME: - cost-effectiveness of prophylaxis with methenamine hippurate for prevention of post-operative UTI compared to prophylaxis with fluoroquinolones - rate of culture-positive symptomatic UTI - prevalence of antibiotic resistance in positive post-operative cultures - prevalence of side effects following a 24-hour course of methenamine hippurate - factors that may influence patient compliance with short-course of chemoprophylaxis. Cost-effectiveness data: We plan to perform a cost-effectiveness analysis from a societal perspective, which will be expressed as incremental cost per UTI prevented. Routine costs of prevention of UTI with methenamine hippurate prophylaxis will be compared with costs of prevention of UTI with fluoroquinolone prophylaxis. We plan to capture incremental direct health care costs, which will be estimated using the resource costing method. Direct medical service standard of care use (such as number and types of physician visits, hospital admissions lengths, emergency transport and emergency room visits), and direct medical costs (such as antibiotic treatment of UTI, prophylaxis with methenamine or ciprofloxacin, urine laboratory tests, or treatment of complications like pyelonephritis) will be monetized by multiplying the number of units of each resource used per treatment arm by the average unit cost of these items in dollars. Detailed individual cost data will not be collected. This method allows a consistent capture of resource use when costs are incurred across multiple health systems or payers. Cost for each direct medical service use, direct non-medical items, and indirect items will be assigned based on national Medicare reimbursement rates or other standardized unit costs. Among patients who undergo urine culture as part of standard of care for UTI, the rate of positive cultures will be identified. As per standard of care, antibiotic resistance will be collected by sensitivity testing on all positive urine cultures identified from samples collected for evaluation of symptomatic UTI in post-operative patients. Bacterial species and sensitivities will be identified and recorded. To determine medication compliance rates, any unused medication will be returned to the office at their post-operative follow-up visit. As per routine care, investigators will also ask patients during the weekly routine post-operative call and routine post-operative visits about their compliance with the second dose of medication. Adverse effects from the administration of methenamine and fluoroquinolones will be collected. Patients will be asked to document any side effects, including nausea, vomiting, pruritis, and rash, that may occur within 24 hours of the administration of the last dose of methenamine or antibiotic.

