## **Protocol**

**Abstract**

Catheter-associated urinary tract infection (UTI) is the most common post-operative nosocomial infection. An agent that prevents catheter-associated UTI but is not associated with antibiotic resistance is not known. Methenamine hippurate has similar pharmacokinetics as short-course antibiotics that prevent catheter-associated UTI, such as ciprofloxacin. Our aim is to compare the efficacy of an innovative short regimen of methenamine hippurate, an antiseptic that is converted into formaldehyde in urine, with the efficacy of short-course ciprofloxacin for preventing post-operative UTI in urogynecologic surgery. We propose a randomized, blinded non-inferiority trial to determine the efficacy of two doses of methenamine hippurate compared with the urology standard of fluoroquinolones at catheter withdrawal for reducing post-operative UTI in patients requiring short-term indwelling catheterization after pelvic reconstructive surgery. The primary outcome will be the rate of symptomatic UTI requiring treatment within three weeks of surgery. We will perform cost-effectiveness analysis comparing the cost of prophylaxis with methenamine to the cost of prophylaxis with ciprofloxacin. We plan to describe the resistance profile of positive urine cultures and adverse effects of methenamine. This study is innovative because it involves 1) a two-dose regimen of a non-antibiotic prophylactic and 2) cost-effectiveness analysis. The findings will help reduce the rate of antibiotic use and nosocomial UTIs, which are associated with morbidity and serve as important indicators of quality of care.

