**Objectives**

**Overall objectives**

SPECIFIC AIMS Primary Aim: To determine if the efficacy of prophylaxis with a 24 hour course of methenamine hippurate (two doses) is non-inferior to the efficacy of a 24-hour course of fluoroquinolones in prevention of post-operative urinary tract infections after short-term indwelling catheterization following surgery for pelvic floor disorders. Secondary aim: - To determine if prophylaxis with methenamine hippurate is more cost-effective than prophylaxis with fluoroquinolones

in patients undergoing short-term indwelling catheterization. - To determine the antibiotic resistance profile of post-operative urinary tract infections that develop after short-term indwelling catheterization after surgery for pelvic floor disorders, with methenamine as compared to fluoroquinolones. - To determine the prevalence of side effects that may accompany use of methenamine hippurate prophylaxis. - To describe factors that influence patient medication compliance with short-term methenamine hippurate and ciprofloxacin prophylaxis.

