**Analysis Plan**

Categorical variables will be analyzed using chi-squared or Fishers exact test and parametric or non-parametric t-tests for continuous variables. Bivariable analysis will be used to determine variables (risk factors) that are independently associated with post-operative UTI. Duration of catheterization between groups will be compared using the Mann-Whitney test to compare difference in medians. The primary outcome will be the rate of clinically suspected UTI requiring treatment within the first three weeks following surgery. Comparison with fluoroquinolones will be performed using relative risk ratio. Analysis will be performed by intention to treat. If imbalances in baseline demographics are identified, multivariate analyses for post-operative UTI will be performed to control the inequality. Cost-effectiveness analysis will be performed by monetizing the collected resource utilization data in each treatment arm, including use of intervention resources, UTI treatment resources, as well as primary and secondary care resources. Incremental cost-effectiveness ratios will be calculated to compare difference in costs between prophylaxis with methenamine and prophylaxis with fluoroquinolones to the difference in effect on the incidence of post-operative UTI. Prevalence of adverse effects will be measured as

percentages. Rate of urine cultures performed by patients treated for symptomatic UTI, as well as the rate of culture-positive UTI will be noted; comparison with fluoroquinolones will be performed using relative risk ratio, with analysis by intention to treat. Positive cultures will be analyzed for percentage of uropathogen type, type of uropathogen showing resistance, and overall percentage of cultures showing resistance.

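### Side effects are collected in both arms, but the endpoint is worded for methenamine only and no between-arm estimate is specified, so post-operative symptoms could be counted as methenamine side effects (low priority)

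*Combined protocol and SAP*

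**What the plan says.** Three places word the side-effect endpoint for methenamine alone:

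- Abstract: "We plan to describe the resistance profile of positive urine cultures and adverse effects of methenamine".
- Overall objectives: "To determine the prevalence of side effects that may accompany use of methenamine hippurate prophylaxis". Of the secondary aims, cost-effectiveness and resistance are set against fluoroquinolones and compliance names both drugs. Only the side-effect aim has no comparator.
- Secondary outcome variable(s), in the list of outcomes: "prevalence of side effects following a 24-hour course of methenamine hippurate".

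Data collection is wider. The same section states: "Adverse effects from the administration of methenamine and fluoroquinolones will be collected". It then describes what is asked: "Patients will be asked to document any side effects, including nausea, vomiting, pruritis, and rash, that may occur within 24 hours", counted from the last dose of either drug. The Procedures section puts the side-effect questions to study participants generally in the weekly calls.

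The Analysis Plan has one sentence specific to this endpoint, beginning "Prevalence of adverse effects will be measured as" and ending with the single word percentages. It names no arm and no contrast. For the culture outcomes the same section specifies: "comparison with fluoroquinolones will be performed using relative risk ratio, with analysis by intention to treat". It also plans a relative risk for the primary outcome. The section opens with a general rule: "Categorical variables will be analyzed using chi-squared or Fishers exact test".

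**The concern.** Women take the study drug at catheter removal, which the Procedures section schedules 24 to 72 hours after the catheter was placed, soon after pelvic surgery. Some nausea, vomiting, itching or rash may occur at that time whichever drug is given. Any event in the window can be recorded, and no rule says who decides whether the drug caused it. A percentage from the methenamine arm alone is therefore a mixture of drug effect and post-operative background.

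The trial holds a randomised group exposed to the same surgery and asked the same questions. As worded, the endpoint does not use it. The protocol relies on such a contrast when it reads earlier work: Potential Study Risks cites the lack of a significant difference in side effects between methenamine and placebo groups.

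Two things are at stake. The methenamine percentage could be read as the drug's side-effect rate. And the trial would have no planned estimate comparing the tolerability of the two options, although Potential Study Benefits mentions minimising adverse effects as a possible advantage of replacing antibiotics.

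**Working it through.** **Sample size per arm.** The documents state no precision or power for side effects, so the planned 120 per arm in Accrual is used. It reproduces from that section's inputs (22% in both arms, margin 15 points, one-sided alpha 0.025, 80% power):

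n = (1.960 + 0.842)² × 2 × 0.22 × 0.78 / 0.15² = 7.85 × 0.3432 / 0.0225 ≈ 119.7, rounded up to 120.

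**Inputs for the illustration.**

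- Methenamine nausea: 3.5% or less (Potential Study Risks). The upper value, m = 0.035, is used and treated as drug-caused, which is an assumption.
- Fluoroquinolone nausea: q = 0.025 to 0.04 for ciprofloxacin and 0.07 for levofloxacin (same section).
- Background post-operative nausea b: not in the documents. Assumed range 2% to 30%.

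**Formulas**, with background and drug effect acting independently:

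- Methenamine-arm percentage: p₁ = b + (1 − b) × 0.035
- Fluoroquinolone-arm percentage: p₂ = b + (1 − b) × q
- Background share of the methenamine-arm percentage: b / p₁
- 95% half-width of the difference: 1.96 × √[p₁(1 − p₁)/120 + p₂(1 − p₂)/120]

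| Assumed b | p₁ | Background share | p₁ − p₂ for q = 2.5% to 7% (points) | 95% half-width (points) |
|---|---|---|---|---|
| 2% | 5.4% | 37% | +1.0 to −3.4 | 5.5 to 6.5 |
| 5% | 8.3% | 60% | +1.0 to −3.3 | 6.8 to 7.6 |
| 10% | 13.2% | 76% | +0.9 to −3.2 | 8.4 to 9.0 |
| 20% | 22.8% | 88% | +0.8 to −2.8 | 10.6 to 10.8 |
| 30% | 32.5% | 92% | +0.7 to −2.5 | 11.8 to 12.0 |

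For b = 30%: p₁ = 0.30 + 0.70 × 0.035 = 0.3245. With q = 0.07, p₂ = 0.349 and the half-width is 1.96 × √[(0.2192 + 0.2272)/120] = 0.120.

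The single-arm percentage moves from 5% to 33% on the background assumption alone. The between-arm difference moves by less than one point for a given q. Its interval is wide throughout and would include zero in every row.

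The Study duration section still gives 72 per arm. At that size the half-widths grow by √(120/72) = 1.29, to about 7 to 15 points.

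**Observation window.** The Secondary outcome section ends the window 24 hours after the last dose. The Procedures section gives levofloxacin as one dose, and ciprofloxacin and methenamine as two doses 12 hours apart. Counted from first dose, the window is about 24 hours for levofloxacin and 12 + 24 = 36 hours for the other two. At the levofloxacin sites the methenamine arm is therefore observed for about 12 hours longer than its comparator.

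**The case against.** The strongest reply is that this is loose wording rather than a missing control. Fluoroquinolone-arm data are collected under the same heading as the outcome. The percentages sentence in the Analysis Plan is not limited to methenamine. The opening chi-squared or Fisher rule could cover side effects by arm. Describing prevalence for a new two-dose regimen is also a legitimate aim in itself.

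Much of this stands. A reader might infer that post-operative symptoms will necessarily be reported as methenamine side effects. The documents do not support that, because nothing restricts reporting to one arm; the supportable word is could. What remains is that the general rule names neither this endpoint nor the groups, and it yields a test rather than an effect estimate, while other binary outcomes receive an explicit comparison.

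A reader might also infer a fixed inflation factor. Backgrounds of 10% to 30% would put the arm percentage at about 4 to 9 times 3.5% (13.2/3.5 and 32.5/3.5), but a 2% background gives only about 1.5 times (5.4/3.5). No document figure selects among these. The nearest evidence, in Potential Study Risks, is 6 methenamine patients with mild effects across 6 studies; without denominators it gives no rate.

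Finally, the comparator is active. The between-arm difference estimates methenamine against a fluoroquinolone and does not isolate methenamine toxicity. The remark in Potential Study Benefits is conditional and is not a hypothesis of the trial.

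**Conclusion.** The point holds as an under-specified comparison. The aim, the outcome and the Abstract name methenamine only, the endpoint-specific analysis is percentages, and a randomised comparator already being collected has no planned effect estimate. Post-operative symptoms could be counted as methenamine side effects.

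The direction holds for any non-zero background if events are not attributed. The size is not known: the 5% to 33% range rests on an assumed background of 2% to 30%, a drug effect at the protocol's upper figure, and independence of the two. The endpoint is secondary and descriptive, and the primary analysis, sample size and eligibility are untouched. Priority is low.

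**What to change.** 1. In Overall objectives and Secondary outcome variable(s), and for consistency in the Abstract, define the endpoint as the proportion with each prompted side effect, and with any side effect, in each randomised arm.
2. In the Analysis Plan, report percentages by arm and the methenamine-minus-fluoroquinolone risk difference with a 95% confidence interval. State that this compares methenamine with an active comparator and is not a measure of pure methenamine toxicity.
3. Define one observation window from the first dose for all participants. Alternatively, report by site or fluoroquinolone; this confines the unequal windows to the levofloxacin sites but does not remove them.

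The cost is some wording and one extra table, with no new participants or visits. A common window needs time of onset to be recorded on the call form. The downside is that the intervals will be wide (half-width about 5 to 12 points at 120 per arm under the assumptions above), so the table will show how little the trial can say about uncommon effects. The wording should be settled before unblinding so that the comparison is not chosen after the data are seen.

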
#### **Background**

URINARY TRACT INFECTIONS ASSOCIATED WITH SHORT-TERM INDWELLING CATHETERIZATION: Catheter-associated urinary tract infection (UTI) is the most common nosocomial infection in the United States. The risk of UTI in women following pelvic reconstructive surgery is 9-48%. Almost 50% women who undergo pelvic reconstructive surgery develop urinary retention that requires short-term catheterization. (2) In a recent study, over 80% women who required catheterization after pelvic reconstructive surgery used an indwelling catheter for at least 24 hours. (5) The risk of bacteriuria is estimated to be 5-10% for each day of indwelling catheterization. (6,7) UTIs occur frequently after catheter removal, (8,9) likely due to dislodgement of bacterial colonization in biofilms in the catheter. COMPLICATIONS AND COSTS ASSOCIATED WITH UTI: Prevention of post-operative UTI is important for both patient and health care systems. UTIs increase the economic

burden on both patients and physicians, as each episode of UTI costs approximately \$600. (10) Complications from short-term catheterization include pyelonephritis, perinephric abscesses, and bacteremia (UTIs are the cause of 15% of all nosocomial bloodstream infections). (11) Catheter-associated UTI (CAUTI) has become costly for hospitals as well; since October 1, 2008, the Centers for Medicare and Medicaid Services (CMS) have not provided hospitals compensation for CAUTIs. (10) As part of hospital quality measurement, the National Healthcare Safety Network monitors and reports CAUTIs, and prevention of CAUTI is one of the National Patient Safety Goals set by the Joint Commission.

**PROPHYLAXIS FOR PREVENTION OF POST-OPERATIVE UTI:** Catheter-associated UTI likely occurs during catheter removal when bacteria colonized in the catheter are dislodged into the bladder. Chemoprophylaxis with antibiotics or antiseptics such as methenamine can potentially decrease the chance of UTI after post-operative catheterization. However, prophylaxis is not routinely used for prevention of urinary tract infections after catheterization. In a study by Wazait et al, 40% of providers involved in the management of indwelling catheters do not use prophylactic antibiotics for catheter removal.(12) A Cochrane review examining the use of prophylactic antibiotics for short-term catheterization showed weak and limited evidence that it reduced the rate of bacteriuria, and suggested caution in interpreting the results because of the limited literature.(13) American Urologic Association (AUA) and the American College of Obstetrics and Gynecology (ACOG) recommend consideration of prophylactic antibiotics for catheter removal, but does not require antibiotic use. AUA guidelines suggest that first-line antibiotics such as either fluoroquinolones (like ciprofloxacin or levofloxacin) or trimethoprim-sulfamethoxazole may be warranted at the time of catheter removal following urinary tract surgery, especially in patients with risk factors such as advanced age, anatomic anomalies, and immunodeficiencies; however, treatment may also be deferred and based on urine culture at catheter removal.(14) ACOG guidelines suggest that daily antibiotic prophylaxis should be considered in women discharged with an indwelling urinary catheter after urogynecologic surgery.(15) The above recommendations for chemoprophylaxis for short-term post-operative catheter use are mostly based on non-gynecologic populations and there are no specific recommendations on the choice and dose of the agent. However, several randomized controlled trials have explored the efficacy of short courses of antibiotic prophylaxis at catheter removal for preventing UTI. In a recent meta-analysis of 7 studies, Marschall et al concluded that antibiotic prophylaxis at catheter removal was beneficial in reducing symptomatic UTI, with subgroup analysis indicating significant benefit in post-surgical patients but not in general mixed hospital populations. (16) Of the four RCT or prospective cohort studies looking at gynecologic or urogynecologic populations solely, 3 showed some benefit to antibiotic prophylaxis, while 1 showed no benefit to antibiotic use.

**(17-20) COMPLICATIONS OF ANTIBIOTIC PROPHYLAXIS:** Though a short course of antibiotic prophylaxis at catheter removal may be effective for preventing post-operative UTI, widespread adoption of antibiotic prophylaxis would increase the risk of antibiotic resistance. Multi-drug resistance is already prevalent in North America; in 2000, the SENTRY study reported that in nosocomial UTIs, rates of antibiotic resistance of four common uropathogens were 59, 31, 43 and 29% for ampicillin, amoxicillin/clavulanate, trimethoprim-sulfamethoxazole, and ciprofloxacin, respectively. (21) The rising cost of increased antibiotic use must also be considered, as well as the potential for adverse medication effects, which can be severe.

**METHENAMINE IS NOT AN ANTIBIOTIC:** A possible alternative to antibiotics is methenamine hippurate, a urinary antiseptic currently used for prophylaxis for recurrent urinary tract infections. The mechanism of action of methenamine hippurate is through the formation of formaldehyde in the presence of acidic urine. Hippurate, also known as hippuric acid, acidifies the urine, which allows for greater production of formaldehyde. Methenamine hippurate is relatively inexpensive at about \$2 per pill (22) (compared to \$3-17 per pill for commonly used antibiotic prophylaxis). (23-25) While resistance to methenamine hippurate can be induced with some difficulty in vitro, it has not been reported in vivo. (26) Daily methenamine reduces UTI after gynecologic surgery: Daily methenamine hippurate throughout catheterization has been shown to be effective for decreasing post-operative UTI after gynecologic surgery .Three studies reported that daily methenamine decreases post-operative UTI as well as post-operative bacteriuria, (2,27,28) while one additional study showed significant difference in bacteriuria but did not report the rate of symptomatic UTI. (29) A Cochrane meta-analysis confirmed that methenamine reduces the risk of post-operative UTI. Two subgroup analysis in mixed surgical and non-surgical populations that excluded the presence of renal tract abnormalities and neurogenic bladder showed significant reduction in symptomatic bacteriuria (RR 0.24, CI 0.07-0.89) and bacteriuria (RR 0.56 CI 0.37-0.83).(30) Subgroup analysis of the effect of treatment less than 7 days, which essentially limited analysis to studies only involving patients with post-surgical short-term indwelling catheter, showed even greater benefits, with the risk ratio for bacteriuria and symptomatic bacteriuria be 0.48 (CI 0.23-0.99) and 0.14 (CI 0.05-0.38), respectively.(30) These studies used a wide variety of regimens of methenamine ranging from 1g to 4g

daily in divided dosages.(30) Duration also ranged widely, generally initiated before catheterization to several days after catheterization, with treatment courses ranging from a minimum of five to as many as thirteen days.(30) INNOVATION Although catheter-associated UTI are an important indicator of quality of care, and health care systems are not reimbursed for these nosocomial infections, an effective agent that prevents catheter-associated UTI but does not increase antibiotic resistance has not been identified. We plan to investigate the efficacy of a short course of methenamine (two doses in a 24-hour period) for preventing UTI after short-term indwelling catheterization. Additionally, investigation of short course antibiotic prophylaxis at catheter removal in the urogynecologic population is innovative, since it is common practice in urology, but has not been studied significantly in the urogynecology population, where commonly daily prophylaxis is given. RATIONALE FOR A 24-HOUR DOSE OF METHENAMINE HIPPURATE: For several reasons, we anticipate that two doses of methenamine hippurate, with the first dose administered 2 hours prior to catheter removal, will reduce the rate of UTI following short-term catheterization, and will be non-inferior to antibiotic prophylaxis with fluoroquinolones. 1) Unlike antibiotics commonly used for UTI prophylaxis, methenamine becomes active only in the bladder, and thus concentrates its full antimicrobial effect in the area of choice. 2) Short courses of antibiotics administered 1-2 hours prior to catheter removal have been shown to reduce the rate of UTI post-catheterization.(9,16) 3) The pharmacokinetics of methenamine is similar to that of antibiotics used in short courses for prophylaxis, such as ciprofloxacin, trimethoprim-sulfamethoxazole (TMP-SMX), and nitrofurantoin. Methenamine hippurate has a half-life of 4.5 hours, and reaches the antimicrobial concentration (MIC of formaldehyde) of 13 microgram/mL 30 minutes to 1 hour after oral intake. A single 2 gram dose will yield 18-60 micrograms/mL (with typical daily doses as one dose every 12 hours). Methenamine is renally cleared, with 90% excreted within 24 hours. (26) Comparable antibiotics have half-lives ranging from 3 - 5 hours (ciprofloxacin), 8-10 hours (TMP-SMX), and 20 minutes-1 hour (nitrofurantoin), with serum drug levels peaking at 20 minutes to 4 hours. (31-33) Elimination is also comparable, ranging from 30-40% in urine (nitrofurantoin), (31) 40-50% in urine (and 20-50% in feces within 5 days for ciprofloxacin), (32) 80%/67% in urine (sulfamethoxazole and trimethoprim, respectively, within 72 hours). (33) 4) Prior studies suggest that acidification of urine by additional acidifying agents is not required for effectiveness of methenamine hippurate. (34) This suggests that two doses of methenamine hippurate, with the first dose initiated 2 hours prior to catheter removal is reasonable and potentially effective for preventing post-operative UTI. Benefits of a 24-hour dose of methenamine: A short course of methenamine hippurate for preventing post-operative UTI will decrease the cost and complications of post-operative UTI; minimize drug resistance, adverse effects and cost of treatment; and likely increase medication compliance. There are currently no studies to demonstrate the effectiveness of a short-course of methenamine hippurate as chemoprophylaxis for post-operative UTI. If successful, a short course of methenamine hippurate would be a revolutionary and attractive non-antibiotic chemoprophylaxis alternative to a short-course of a commonly used antibiotics such as the fluoroquinolones or a longer course of methenamine. Justification for Non-Inferiority Trial We believe that a non-inferiority trial between two active arms would be more clinically useful than a placebo-controlled trial. As stated above, both methenamine and fluoroquinolones (such as ciprofloxacin or levofloxacin) are accepted to be effective in reducing the rate of bacteriuria. Additionally, current urology practice is to give a first-line antibiotic (either the fluoroquinolones or trimethoprim-sulfoxazole) at catheter withdrawal at prophylaxis. Our study is innovative in that this is not current standard practice in urogynecology; having two active arms would change antibiotic use in urogynecology by showing the effectiveness of a lower dose of antibiotic prophylaxis for catheter removal, as well as comparing this to the effectiveness of an antibiotic alternative for catheter removal prophylaxis in the urogynecologic population. Both of the results from these active arms would help to decrease use of antibiotics in current urogynecology practice.
